|----------------|-------------------------|--|---|--|---|---------------|
| Eligible sites | | training outcomes | INTERVENTION DELIVERY | Professional post- workshop outcomes | Professional qualitative interviews | |
| | Control cluster | Intervention cluster | Patients entering the service Routine data (Baseline-last treatment session) | | Enriched data 6mth outcomes | Enriched data |

USUAL CARE

Patients entering the service

The following table (Table I) provides an overview of trial activities and timelines for the EQUITy trial, most of which relate to the intervention arm. Further information about the enriched patient sample follows the table.

Table I

| ENTRY INTO | I-day service guidelines team | |
|---------------|--|---|
| Week I | workshop (PWPs, service leads, admin staff etc) | |
| Weeks 2 – 3 | Practitioner telephone training Two 3-hour training sessions held on separate days | Weeks 2 - 24 Distribution of patient resources (electronic |
| Weeks 6 – 8 | 45-60-minute action plan lead/team follow-up meeting online or via telephone | and/or hard copies dependent on service preference) |
| Weeks 10 - 24 | Offer of additional follow-up meetings online or via telephone | Weeks 3 - 24 |
| Weeks 16 – 24 | Qualitative interviews/discussion groups with patients and professionals | Recruitment of an enriched patient sample (intervention and control arms) |

Sites will be informed of their allocation approximately I month prior to their chosen intervention dates (Trial Entry Date). Regardless of the trial arm they are allocated to, the Trial Start Date for each service will be the date of their chosen workshop (the initial delivered component of the intervention).

EVALUATION

The trial design is embedded in routine IAPT services and takes advantage of data that is available through IAPT operations, supplemented by bespoke research data. IAPT datasets are comprehensive at baseline with consequent high external validity [Gyani et al 2011]. However, they lack long term outcomes, as services do not follow up service users after discharge. Additionally, they do not collect broader service use measures and generic, preference-based health status measures.

In order to effectively and efficiently evaluate the long term and economic impact of the EQUITy intervention, we will combine routine IAPT data with additional data from consenting patients from the intervention and control sites (see Figure 1).

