The addition of the EQUITy intervention, compared with usual routine IAPT care, will therefore be evaluated (via patient and professional measures) in a number of different ways.

- I. Routine IAPT data
- 2. Enriched data set
- 3. Pre-post workshop questionnaires/measures
- 4. Pre-post telephone training questionnaires/measures
- 5. Qualitative interviews

Detail about each of these activities/methods are included below, further details of the outcome measures for each is included in Section 6.

I. Routine IAPT data

The 'Routine Data Sample' will include all those patients entering each IAPT service, taking advantage of data that IAPT already collects. This data is comprehensive (as it includes all patients) but limited in scope (as they exist at baseline and end of treatment only and lack measures of certain important issues).

IAPT collects outcome measure data on a session-by-session basis for every patient who receives treatment, delivered via all modalities (i.e. face-to-face, telephone, internet). We will request data from services for 12 months pre and 12 months post implementation of the EQUITy trial. The start date of the intervention at each of the intervention arm sites will be the day of the initial workshop. Box 4 provides detail on the data collected as part of the routine IAPT Data Set (for more detail please see Appendix 1):

[figure not shown]
Box 4 Routine IAPT data

Descriptive data

patient demographics (including geographical locations, gender, age, employment, ethnicity, language, religion, sexual orientation and disabilities); care pathway referral details, mental health care cluster details; information on presenting complaints (mental and physical); sessions attended/unattended; intervention details; clinical, economic and social outcomes; waiting times and practitioner qualifications.

Treatment engagement

treatment attendance and duration data including: Date of referral, Date of Assessment, Date Start of Treatment, Date End of Treatment, Number of Sessions attended/unattended, Reason for Termination.

Outcomes

Patient Health Questionnaire [PHQ-9; Kroenke et al 2001] for depression, Generalised Anxiety Disorder scale [GAD-7; Spitzer et al 2006] for anxiety, IAPT Phobia Scale [IAPT Data Handbook, Appendix D3 2011], and the Work and Social Adjustment Scale [WSAS; Mundt et al 2002] for functioning.

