We are interested in exploring the data associated with patients accessing Step 2 treatment, which may include information of if they have been stepped up to receive Step 3 treatment. Some services may not be able to manually extract only the data requested by the research team from the dataset that they submit regularly to NHS England and thus they will be unable to exclude any subsequent Step 3 service data in the dataset they provide. This is due to resource and time issues. They will, however, be able to remove any patient identifiers such as full date of birth and postcode, ensuring that the date set remains pseudonymous. If this occurs the research team will manually remove any irrelevant Step 3 data. The data that they submit to NHS England is made available in the public realm thus no concerns have been identified about the sharing of this data.

Patients – enriched sample

As a pragmatic trial of a model of a service quality improvement intervention, the inclusion criteria are simple to enhance the external validity of the study. All adults (18+) accessing telephone-delivered Step 2 treatment following randomisation (intervention or control arm) will be eligible to participate in the enriched sample.

All patients who enter a service and are referred to telephone treatment will be invited to consent to being part of enriched data sample (although we will restrict the numbers in

that sample in each site). Recruitment will continue for a maximum of 9 months at each site to allow for as close to 100 patients consenting to participate.

Patients – post-intervention implementation qualitative interviews

We will purposively sample across all the services allocated to receive the EQUITy intervention (i.e. 11) to ensure variance in clinical and organisational contexts. A sampling frame will capture patients with different clinical profiles (diagnosis, severity) and levels of intervention engagement (e.g. no sessions attended, first session only, multiple sessions) Maximum variation sampling will ensure patients of different socio-economic background, age, ethnicity and gender are included.

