Patients in the intervention cluster will be exposed to telephone treatments which has been influenced by the EQUITy intervention, although decisions made with patients regarding their treatment will not be influenced directly, and no new treatments will be introduced.

Participants taking part in trials usually provide written informed consent for a range of research procedures, including participation and data collection. However, seeking patient consent for all research procedures is not always appropriate. As the the EQUITy intervention will be offered to all PWPs and other staff members working in those services (i.e. service leads, managers, supervisors, administrators), all patients receiving telephone treatment after delivery of the EQUITy intervention have the potential to be 'exposed', and this exposure is not under their control. However, as detailed previously, the intervention is a service quality improvement intervention, not the introduction of a new treatment. Furthermore, data collected by IAPT services currently is shared by services anonymously and used for evaluation and monitoring processes.

Patients - Enriched Data Sample

As noted above, a sub-sample of patients (up to 100 per site) entering the service (intervention and control arms) during the trial will be invited to participate in a more detailed data collection as part of the Enriched Data Sample.

Eligible patients (those offered a Step 2 telephone treatment) will be identified from the computer systems at intervention and control arm IAPT services. All patients who are allocated to receive treatment by telephone will be sent a patient information pack

(electronic or postal, dependent on service/patient-preferred means of communication) containing a patient invitation letter, an information sheet, a consent to contact form and consent form. Packs sent electronically will include a link to the online consent to consent to contact form that can be returned if they wish to contact the research tream prior to consenting. Anyone who is interested in taking part can return the consent to contact form by email to the research team or email/phone the research team directly, prior to providing consent.

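### The protocol gives conflicting start points for enriched-sample eligibility, and the formal criterion, read literally, opens before any intervention component exists.

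*Protocol*

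**What the plan says.** The protocol places the start of enriched-sample eligibility in four ways.

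- **Section 6.1, Patients – enriched sample:** "All adults (18+) accessing telephone-delivered Step 2 treatment following randomisation (intervention or control arm) will be eligible to participate in the enriched sample".
- **Section 5.2, Table I:** the cell reads "Offer of additional follow-up meetings online or via telephone | Weeks 3 - 24", followed by "Recruitment of an enriched patient sample (intervention and control arms". The table is broken in extraction, but the parallel cell giving weeks 2–24 for patient resources supports reading weeks 3–24 as the enriched recruitment window. The workshop is in week 1 and practitioner training in weeks 2–3.
- **Section 6.3, Intervention clusters:** the date of entry is glossed as one week after the trial start date. The matching text for control clusters has no such gloss.
- **Section 6.2, Patients:** eligibility belongs to adults referred to Step 2 telephone treatment in the trial period, which is not defined.

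Two statements after Table I fix the timeline. On allocation: "Sites will be informed of their allocation approximately I month prior to their chosen intervention dates (Trial Entry Date". On the start, whichever the arm: "the Trial Start Date for each service will be the date of their chosen workshop (the initial delivered component of the intervention". Section 6.3 describes possible exposure in terms of delivery: "all patients receiving telephone treatment after delivery of the EQUITy intervention have the potential to be 'exposed".

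The end of recruitment also varies. It is week 24 in Table I, at most 9 months in section 6.1, and between 6 and 9 months in section 6.2.

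**The concern.** The only sentence in section 6.1 that works as an inclusion criterion for the enriched sample is tied to randomisation, not to the Trial Start Date. Randomisation comes before notice of allocation, and notice comes about a month before the workshop. In that interval an intervention site has had no workshop, no guidelines, no training and no patient resources. A patient who enters then meets the criterion as worded and would be analysed in the intervention arm, although section 6.3 ties possible exposure to treatment after delivery.

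Two things are at stake. Pre-workshop patients would pull the estimate towards zero. And because the sections disagree, sites could open at different points relative to the intervention and each claim to follow the protocol.

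**Working it through.** **1. Timeline, with the Trial Start Date (workshop, week 1) as time zero.**

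| Source | Start of eligibility or entry |
|---|---|
| Section 6.1 | Randomisation, so no later than notice of allocation: about −1 month = −4.3 weeks, or earlier |
| Section 6.3, intervention clusters | +1 week |
| Table I | Start of week 3 = +2 weeks |
| Section 6.2 | Trial period, undefined |

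Between the earliest and latest dated starts lie about 4.3 + 2 = 6.3 weeks.

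**2. Can Table I simply be taken as controlling?** Weeks 3–24 are 22 weeks. Section 6.2 gives a minimum of 6 months (26 weeks) and section 6.1 a maximum of 9 months (39 weeks). The Table I window therefore conflicts with the text at its end as well as its start.

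**3. Share of pre-workshop patients under the literal section 6.1 reading.** Assume recruitment opens at notice of allocation and accrual is even until closing. Share = 4.3 / (4.3 + closing week).

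- Closing at week 24: 4.3 / 28.3 = 0.152.
- Closing at week 39: 4.3 / 43.3 = 0.099.
- Under the Table I start: 0.

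If the window is counted from the opening date instead, 4.3 / 39 = 0.110 and 4.3 / 26 = 0.165.

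**4. Dilution if pre-workshop patients gain nothing.** Diluted SMD = 0.20 × (1 − share).

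- 0.20 × (1 − 0.099) = 0.180.
- 0.20 × (1 − 0.152) = 0.170.
- Counted from opening: 0.178 and 0.167, so the rounded range stays 0.17–0.18.

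**5. What that means for power.** Section 7.2 states 85% power for an SMD of 0.2, with 11 clusters per arm, ICC 0.027, baseline correlation 0.5, mean cluster size 607 and coefficient of variation 1.14. Two-sided alpha of 0.05 is my assumption.

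- L = 607 × 0.027 / (607 × 0.027 + 0.973) = 0.944.
- Design effect with minimum-variance weights = (1 + 606 × 0.027) / (1 − 1.14² × 0.944 × 0.056) = 18.6.
- Effective n per arm = 11 × 607 / 18.6 / (1 − 0.5²) ≈ 478.
- Power from a noncentral t with 20 df = 83.6%, close to the stated 85%. At ICC 0.04 it is 69.4%, against the stated 70%.

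On this basis power falls to 75% at 10% dilution and 71% at 15%. With equal clusters of 100 and the normal approximation it is 81%, falling to 72% and 67%.

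**The case against.** The strongest reply is that the operating text already sets a later start. Table I opens enriched recruitment at week 3 in both arms, after the workshop, and the Trial Start Date in both arms is the workshop date. Following randomisation is literally true of week 3, so section 6.1 can be read as an outer limit. No sentence tells a site to open at allocation. This stands as far as it goes: a site working to Table I enrols nobody before the workshop. It does not remove the conflict, because Table I disagrees with the text on the closing date too and section 6.3 gives another start.

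A reader might infer from the word *accessing* that patients already in mid-treatment are enrolled. The documents do not support that. The next sentence of section 6.1 invites people who enter a service and are referred. Section 6.2 speaks of referral. Section 5.2 approaches patients as they begin with the service, and section 7 (Data collection) seeks consent at service entry or start of treatment. These passages restrict the stage of care. They do not set a calendar date, so they leave the pre-workshop entrant untouched.

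A reader might also count everyone before the end of week 3 as unexposed, which gives larger shares. That goes too far: the workshop and guidelines arrive in week 1 and patient resources from week 2, so someone referred in weeks 2–3 can meet two of the three components.

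Finally, the workshop-day start for routine data might look like one more conflicting eligibility date. It defines a data request for a different sample. How episodes that straddle that day are handled can be left to the statistical analysis plan.

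**Conclusion.** The conflict is real and should be resolved in the protocol. The consequence is conditional: pre-workshop patients *can* be counted as intervention patients under the section 6.1 wording, but nothing shows that they are.

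The size runs from 0% of the enriched intervention sample, if sites follow Table I, to about 10–15% if they open at notice of allocation. The upper end would take an SMD of 0.20 to about 0.17–0.18. It assumes even accrual to the closing date, a gap of 4.3 weeks and no benefit at all in early entrants. The last assumption is what makes it an upper bound for this scenario, since some later sessions could be with trained staff. A longer gap between randomisation and notice, or a site that reached its cap of 100 early, would raise the share. The documents give no figures for either.

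**What to change.** Replace the section 6.1 sentence with one rule for newly referred patients, the same in both arms and anchored to the existing Trial Start Date. For example: *Eligible patients are adults (18+) newly referred to Step 2 telephone treatment on or after the start of week 3 from the site's Trial Start Date.* Another fixed week would serve equally well, provided it is the same for every site.

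Then align Table I (section 5.2) and sections 6.1, 6.2 and 6.3. Define or drop the trial period in 6.2, remove or correct the one-week gloss that appears only for intervention clusters in 6.3, and settle the end of recruitment (week 24 or 6–9 months).

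Do not tie eligibility to actual completion of training in the intervention arm only. Training can slip after randomisation, and the two arms would then recruit over different windows.

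The cost is small: wording, plus a filter on the referral date, which Appendix I already lists and services hold. A few early patients are not counted. Control sites need nothing new, as they already have a Trial Start Date.

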Dependent on patients' presenting symptoms a disorder-specific assessment questionnaire(s) may also be collected that include: Social Phobia Inventory [SPIN; Connor et al 2000], Impact of Events Scale – Revised [IES-R; Weiss 2007], Mobility Inventory [MI; Chambless et al 1985], Obsessive-Compulsive Inventory [OCI; Foa et al 1998], Panic Disorder Severity Scale [PDSS; Shear et al 1997], Francis Irritable Bowel Scale (Francis et al 1997) or The Chalder Fatigue Scale [Cella & Chalder 2010].

IAPT Employment Status Questionnaire, Patient Assessment Experience Questionnaire, Patient Treatment Experience Questionnaire.

2. Enriched Data Sample

We will also recruit a 'Enriched Data Sample' of patients from within the wider 'Routine Data Sample'. These patients will be approached for consent at the beginning of their engagement with the service. We will access baseline and end-of-treatment outcomes from the routine IAPT data, and then collect additional outcomes 6 and 12 months after they enter the trial.

The 'Enriched Data Sample' will be a selected group of patients (selected in terms of patient agreement to provide data). However, the selection will likely be the same in both intervention and control clusters and thus will serve as a robust basis for comparison. The main advantage of the 'Enriched Data Sample' is that it will provide more extensive data over the longer-term.

Patients who consent to be included in this sample will complete the following measures at 6 and 12 months:

6 months only

Agnew Relationship Measure [ARM-5; Agnew-Davies et al 1998, Cahill et al 2012].
 Adapted, by permission of the authors, for the EQUITy trial.

6 and 12 months

• Patient Health Questionnaire [PHQ-9; Kroenke et al 2001] for depression

- Generalised Anxiety Disorder scale [GAD-7; Spitzer et al 2006] for anxiety.
- EQ-5D-5L [Herdman et al 2011]
- Economic Patient Questionnaire (EPQ)

Measures will be completed by patients electronically. It is estimated they will take approximately 15-20 minutes to complete. Layout and presentation of the measures was verified by the EQUITy LEAP to confirm ease of understanding and accessibility in terms of layout and presentation, along with language, layout and wording of the EPQ.

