Interviews/group discussion will be conducted by a Research Associate trained and experienced in taking consent and qualitative methods. Consenting patients will be interviewed for up to one hour at a convenient time over the telephone or via video-call (using Zoom or Microsoft Teams) pending on preference. Consenting professionals will have the option of an interview or group discussion. Interviews will take place by telephone or video-call (using Zoom or Microsoft Teams) pending on professional's preference. Group discussions will take place over Zoom or Microsoft Teams. Telephone interviews will be recorded, with consent using an encrypted digital recorder and transcribed verbatim. Video-calls will be recorded with consent and the video will be immediately destroyed and only the audio will be kept and transcribed..

Table 2 provides information regarding the collection of the evaluation data for patients, while Table 3 provides information about the professional measures, further information can be found in Sections 6.1-6.3.

Table 2. Schedule of enrolment and data collection for patients (intervention and control arms).

| | Study Period | | | | |
|--------------------------------------|--------------|----------|-----------|-----------|-----------|
| | Enrolment | Baseline | End of | 6 months | 12 months |
| | | | Treatment | follow-up | follow-up |
| | | | | (Enriched | (Enriched |
| | | | | Sample) | Sample) |
| Intervention and Control Arms | | | | | |
| Consent to be contacted (Enriched | X | | | | |
| sample) | | | | | |
| Informed Consent (Enriched sample) | Х | | | | |
| Identifiable Data | | | | | |
| Date of birth (Enriched sample) | X | | | | |
| Primary Outcome Measures | | | | | |
| Patient Health Questionnaire (PHQ-9) | | X | X | X | X |
| Generalised Anxiety Disorder scale | | X | X | Χ | Х |
| (GAD-7) | | | | | |
| Secondary Outcome Measures | | | | | |
| Patient Demographics | | X | | | |

[figure not shown]
| IAPT Phobia Scale | X | | | |
|--|------------|---|----------|---|
| Work and Social Adjustment Scale | X | | | |
| EQ-5D-5L | | | Х | |
| Agnew Relationship Measure (ARM-5) | | | Х | X |
| Economic Patient Questionnaire (EPQ) | | | X | X |
| Social Phobia Inventory (SPIN) | X * | | | |
| Impact of Events Scale – Revised (IES-R) | X * | | | |
| Obsessive-Compulsive Inventory (OCI) | X * | | | |
| Panic Disorder Severity Scale (PDSS) | X * | | | |
| Francis Irritable Bowel Scale | X * | | | |
| Chalder Fatigue Scale | X * | | | |

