| Additional Information | | | | |
| IAPT Employment Status questionnaire | X | | | |
| Patient Assessment Experience | X | | | |
| Questionnaire | | | | |
| Patient Treatment Experience | | X | | |
| Questionnaire | | | | |
| Number of sessions attended | | X | | |
| Intervention Arm only | • | • | . | • |
| PWP who delivered telephone sessions | | X | | |
| Additional participation | | | | |
| Qualitative interview | | X | | |

X = Data collected routinely by services; X = Data collected by the research team; * = Collection of this measure is dependent on the patient's presentation

Practitioners who are involved in the intervention arm sites will be asked to complete before and after workshop and training measures to explore impact and acceptability of the EQUITy intervention. They will also be invited to take part in a qualitative interview. Practitioners who are working in a site allocated to the control arm will not be asked to take part in any data collection or feedback activities.

Table 3. Schedule of enrolment and data collection for professional data (intervention and control arms).

[figure not shown]
| | Study Per | Study Period | | |
|---------------------------|--------------|---------------|--|--|
| | Pre-activity | Post-activity | | |
| Intervention Arm Activity | • | • | | |
| Team Workshop | | | | |
| Demographic questionnaire | X | | | |

| COM-B | X | X |
|----------------------------|---|---|
| ORIC | X | |
| | | |
| | | |
| Telephone Training | | |
| Demographic questionnaire* | Х | |
| COM-B | X | X |
| TARS | | X |

^{*} if they have already completed this at the first team workshop, they will not be asked to complete this again.

STUDY PARTICIPANTS

6.1 Inclusion Criteria:

Services

Any IAPT service (NHS or third sector) who supports patients at Step 2 over the telephone will be eligible. Services will need to be providing at least 20% of their treatment sessions using the telephone and have enough referrals likely to allow for a sample of 100 patients for the enriched sample (aim to achieve 100 but not a compulsory condition of involvement).

Multiple IAPT services within the same Trust will be included if they work independently to each other.

Patients

Patients - Routine IAPT dataset

[figure not shown]
We will request pseudonymous IAPT routine data of all patients who access the service, irrespective of which treatment modality they are referred to (12 months of data pre-intervention implementation).

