If relevant, based on patients' presenting symptoms, these may also include:

- Social Phobia Inventory (SPIN; Connor et al 2000), Impact of Events Scale –
 Revised (IES-R; Weiss 2007), Mobility Inventory (MI; Chambless et al 1985),
 Obsessive-Compulsive Inventory (OCI; Foa et al 1998), Panic Disorder Severity
 Scale (PDSS; Shear et al 1997), Francis Irritable Bowel Scale (Francis et al 1997) or
 The Chalder Fatigue Scale (Cella & Chalder 2010).
- b) Patient engagement will be measured by routinely collected treatment attendance and duration data from the IAPT routine data. The number of sessions attended/unattended will be the primary source of data. Other data to corroborate this will include dates referred, assessed, started and ended -treatment and also reason for termination.
- c) Service engagement will be measured by numbers attending the team workshop, telephone training, and implementation of the action plan prepared at the first workshop. Organisational readiness for change will be measured by asking workshop attendees to complete the ORIC.
 Professional behaviour change will be monitored using the COM-B questionnaire.

Enriched Data Sample (patients)

[figure not shown]
The enriched data sample will complete additional measures (as detailed below) at 6 and 12 months, following their initial appointment.

Primary outcomes (6- and 12-month follow-up)

The severity of mental health symptoms will be measured using the Patient Health Questionnaire [PHQ-9; Kroenke et al 2001] for depression and the Generalised Anxiety Disorder scale [GAD-7; Spitzer et al 2006] for anxiety. Primary outcome measures will be collected at 6- and 12-months follow-up.

Baseline and end of treatment outcome measure data will be obtained and matched with the 6 and 12-month follow-up data, with patient consent, from the Routine IAPT data set.

Therapeutic Relationship (6-month follow-up only)

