IAPT datasets are comprehensive at baseline with consequent high external validity [Gyani et al 2011]. However, they lack long term outcomes; services do not follow up service users after discharge. Additionally, they do not collect broader service use measures and generic, preference-based health status measures.

To overcome this, we will seek patient consent at service entry/start of treatment, to collect 6 and 12-month follow-up data for a sub-sample of patients (up to 100 per service), via mail or online, with or without telephone support, for a minimum outcome set: depression and anxiety symptoms (PHQ-9, GAD-7), health status (EQ-5D-5L), a brief measure of health and social care service use (EPQ), and, at 6 months only, the Agnew Relationship Measure (ARM-5) of patient alliance ratings of telephone-treatment sessions.

Clinical Trials Unit Involvement

The main data collection method will be online completion of the measures directly into a Clinical Trials Unit (CTU) database (Manchester CTU,

https://www.bmh.manchester.ac.uk/research/manchester-ctu/). Manchester CTU will be responsible for data management of the Enriched data sample using their Electronic Data Capture Database.

Following gathering patient consent (by the research team), which will include obtaining consent to share name, contact details and service location with Manchester CTU, patient details will be passed to the CTU who will register the patient with the trial and allocate an ID.

Participants will be sent an email prepared by the EQUITy research team automatically by the CTU via email to complete the follow-up measures (6 or 12-month) online. If, at the time of consent patients indicated they are adverse to completing measures electronically (online/email), telephone contact will be made by the research team dependent upon the participant's needs. Online follow-ups will be supported by telephone reminders from the research team should deadlines for completion be missed. All losses to follow-up, withdrawal and loss of contact will be fully recorded and reported.

Participants will receive a small thank you (£5 gift voucher at each follow-up time point) to support all methods of follow-up at 6 and 12 months, with circulation of incentives dependent upon method of completion.

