Although the exact details of the analysis will be in that plan, the broad analysis will be as follows. We will assess the intervention's cost-effectiveness at two levels. The first (within-study analysis) will assess whether the intervention is cost-effective in the services and participants included in the implementation trial. The second (decision analysis) will explore potential cost-effectiveness outside the trial setting. Both analyses will use a cost-effectiveness acceptability approach to generate a cost-effectiveness acceptability curve, estimate the likelihood that the intervention is cost-effective, and calculate the net benefit statistic [Briggs & O'Brien 2001; Fenwick et al 2001; Hoch et al 2002; Pedram Sendi & Briggs 2001].

Within-study analysis: The primary analysis will use the NHS and Personal Social Services Perspective, (recommended by NICE) and time horizon of 6-months from 6-month follow-up to end of scheduled follow up (12-months). Regression analysis with bootstrapping, controlling for key covariates will estimate the net costs and QALYs of the intervention and generate a cost-effectiveness acceptability curve [Briggs and O'Brien 2001; Fenwick et al 2001; Hoch et al 2002; Pedram et al 2001], estimate the likelihood the intervention is cost-effective at a willingness to pay threshold of £15,000, and the net benefit statistic.

We will combine psuedonymised, routine IAPT data with the EQ-5D-5L [Herdman et al 2011] and health and social care service use data collected from participants at 6 and 12-month follow-up. The Economic Patient Questionnaire (EPQ) used in the NIHR funded EQUIP programme will be adapted to collect data about use of non-IAPT services (e.g. hospital, CMHT, primary care, social services and third-sector care). Questions about non-NHS & social care services paid for by the participant and paid/unpaid employment will be included for sensitivity analysis.

Costs will be estimated as service use multiplied by published unit cost, by type of service [PSSRU 2017, Department of Health 2017]. Intervention costs will include the costs of providing the intervention and annual equivalent cost developing intervention components. QALYs will be estimated from EQ-5D-5L responses and published utility-tariffs [van Hout et al 2012; Devlin et al 2018].

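### Table 2 marks the EQ-5D-5L at 6 months only and the ARM-5 at 6 and 12 months, the reverse of the schedule in the protocol text

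*Protocol*

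**What the plan says.** Table 2 (section 5.2) is the schedule of enrolment and data collection for patients in both arms. Its EQ-5D-5L row carries a single mark, in the 6-month column. The next row reads "Agnew Relationship Measure (ARM-5) | | | Х | X", with marks in the 6- and 12-month columns.

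The text gives the other schedule wherever it mentions these measures:

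- Section 5.2, Enriched Data Sample: the ARM-5 stands alone under a 6-months-only heading, and "EQ-5D-5L [Herdman et al 2011" is listed under the heading for both visits.
- Outcome measures section: the ARM-5 is headed "Therapeutic Relationship (6-month follow-up only", while the economic evaluation, which names the EQ-5D-5L and the EPQ, is headed as 6- and 12-month follow-up.
- Data collection section, Enriched Data Sample: the set for both follow-ups includes "health status (EQ-5D-5L), a brief measure of health and social care service use (EPQ), and, at 6 months only, the Agnew Relationship Measure (ARM-5".
- Section 7.1, Economic evaluation: EQ-5D-5L data come from both follow-ups, QALYs are estimated from them, and the within-study analysis has a "time horizon of 6-months from 6-month follow-up to end of scheduled follow up (12-months".

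**The concern.** A schedule table is an operative part of a protocol, and staff often work from it. The Clinical Trials Unit emails follow-up requests automatically and participants answer online into its database, so an item left off the 12-month form would be left off for everyone.

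The within-study economic analysis needs a utility at each end of its interval, month 6 and month 12. Under Table 2 the second is never requested. The same form would send the ARM-5 at 12 months, although the outcome measures section says its wording was modified for the 6-month point. A 12-month response that was never requested cannot be recovered later.

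**Working it through.** **Step 1: which column is which.** In the extracted text, the part of Table 2 holding these rows has no header and four cells per row; the part with a header has five columns (enrolment, baseline, end of treatment, 6 months, 12 months). Rows with a known visit fix the four cells:

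- "IAPT Phobia Scale | X" puts a routine intake measure in cell 1, so cell 1 is baseline.
- "Number of sessions attended | | X" puts a count known only once treatment is over in cell 2, so cell 2 is end of treatment.
- Cells 3 and 4 are therefore 6 and 12 months. The missing column is enrolment.

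Dropping the 12-month column instead would place the number of sessions attended at baseline, which makes no sense.

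**Step 2: table against text.**

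| Measure | Table 2 | Text |
|---|---|---|
| EQ-5D-5L | 6 months | 6 and 12 months |
| ARM-5 | 6 and 12 months | 6 months |
| EPQ | 6 and 12 months | 6 and 12 months |

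The EPQ row, "Economic Patient Questionnaire (EPQ) | | | X | X", comes straight after the ARM-5 row and agrees with the text. A sideways shift of the columns would have moved it too. The pattern is that of one 12-month mark sitting one row too low.

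**Step 3: what the within-study analysis needs.** The protocol gives no QALY formula. Taking the usual area under the curve over half a year, with U6 and U12 the utilities at months 6 and 12:

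QALY = 0.5 × (U6 + U12) / 2

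With d6 and d12 the between-arm differences in utility, the incremental QALY is 0.5 × (d6 + d12) / 2. For illustration only, assume d6 = 0.03:

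- difference persists (d12 = 0.03): 0.5 × 0.06 / 2 = 0.015
- difference fades (d12 = 0): 0.5 × 0.03 / 2 = 0.0075
- difference reverses (d12 = −0.03): 0.5 × 0 / 2 = 0

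Carrying month 6 forward returns 0.5 × 0.03 = 0.015 in all three cases. It assumes the answer to the part of the question that month 12 was meant to settle.

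**Step 4: is there a substitute?** None is stated.

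- The protocol itself says that routine IAPT data lack generic preference-based measures. The EQ-VAS listed in Appendix 1 is not a utility.
- Section 7.1 plans multiple imputation by predictive mean matching, treating missing data as missing at random. That method borrows observed values, and here no participant would have a 12-month value to lend.

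**Step 5: extent.** In that scenario the 12-month utility is absent for the whole enriched sample, planned at 22 services × 100 patients = 2,200, in both arms alike.

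**The case against.** The strongest reply is that the protocol leaves no doubt about its intention. Every textual statement agrees, including the data collection section that goes on to describe the Clinical Trials Unit's database. Table 2 is introduced as an overview, with the reader sent elsewhere for more detail. Nothing says the table governs or that the electronic form is built from it. This stands, and it makes the harm conditional.

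A second reply is that the mismatch may come from PDF extraction. The table is broken, its header is lost in this part, and its legend now shows the same symbol for routine and research-collected data, so formatting has gone. The anchor rows fix the columns but cannot prove that a mark lies in the right row, and the two rows are adjacent. This also stands in part. The neighbouring rows read correctly and every row has the right number of cells, which makes a drafting slip the likelier cause, but the original PDF should be checked first.

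A reader might go further and infer that the QALY analysis cannot be computed, or that the 12-month utilities will be lost. The protocol does not support that: a form built from the text would be right, and even without month 12 a figure could be produced under an added assumption. Nor can a monetary loss be stated, because the documents give no expected utility difference.

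**Conclusion.** Table 2 is wrong as written in two rows, on the reading that the extracted marks are those of the original. The size is two cells: a missing 12-month mark for the EQ-5D-5L and a surplus one for the ARM-5. If the table were followed, the loss of the 12-month utility would be complete and irreversible, and the month 6 to 12 QALY estimate would rest on an unstated assumption. If the text is followed, nothing is lost.

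The consequence falls on cost-effectiveness, which section 4.2 makes a secondary objective. PHQ-9 and GAD-7 are marked at baseline, end of treatment, 6 and 12 months, and neither they nor the sample size depends on these rows. A reader might therefore be tempted to treat this as a threat to the trial's main result; it is not. Moderate severity is right: low cost, clear error, conditional harm.

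**What to change.** Check Table 2 in the original PDF. If the marks are as extracted, correct two rows: EQ-5D-5L at 6 and 12 months, ARM-5 at 6 months only. The text needs no change. Then compare the Clinical Trials Unit's 6- and 12-month electronic forms with the text, before the first 12-month request goes out if that is still possible. If any 12-month requests have already gone out without the EQ-5D-5L, record how many and state in the economic analysis plan how those utilities will be handled.

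The cost is one table correction and one check of the electronic forms. Patients are asked nothing beyond what the text already describes.
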